8. RESEARCH QUESTION AND OBJECTIVES

The research questions are:

- 1. Are there any differences in the risk of major bleeding between apixaban and warfarin for patients with higher bleeding risk(s) in the general practice settings in Japan?
- 2. Are there any differences in the risk of stroke/systemic embolism between apixaban and warfarin for patients with higher bleeding risk(s) in the general practice settings in Japan?

The primary objective of the study is to compare effectiveness (a composit risk of stroke/SE) and safety (major bleeding events) of warfarin and apixaban among NVAF patients with at least one bleeding risk (that is, patients at higher risk of bleeding)

The secondary objectives are:

- 1. to compare the risk of major gastrointestinal or intracranial bleeding between warfarininitiators and apixaban-initiators in patients with at least one bleeding risk.
- 2. to compare the risk of ischemic stroke, hemorrhagic stroke or SE between warfarininitiators and apixaban-initiators in patients with at least one bleeding risk.

Objectives of other exploratory analysis are to explore the risk of major bleeding and stroke/SE in the specific populations at higher bleeding risk(s).

In this study, predetermined high bleeding risk subgroups are 1) patients with hypertension diagnosis, 2) patients with liver dysfunction, 3) patients with renal dysfunction diagnosis, 4) patients with a history of beleeding, 5) patiens with hemorrphagic stroke, 6) patients with alcohol abuse, 7) patients with concomitamt used of antiplatelet drugs, 8) patients with chronic (continuously for longer than 90 days) comcomitant use of NSAID, 9) highly elderly (> 80 years old), 10) patients with refractory hypertension, 11) patients with a history of peptic ulcer diagnosis, 12) patients with active cancer, 13) patients with diabetes mellitus, 14) patients whose body weight is <40kg, 15) patients with polypharmacy.

In the previous feasibility analysis, we found that the numbers of patients with hemorrhagic stroke, alcohol abuse, chronic concomitant used of NSAIDs (for continuously > 90 days), and refractory hypertension were less than 2,000. Due to the insufficient statistical power, we will not include these subgroups for the future analysis.

Subgroups to be analyzed for exploratory analysis will be described in a SAP.

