First, all patients with NVAF who are newly diagnosed and initiated apixaban or warfarin will be extracted from the database. Among these patients, patients with at least one predetermined high bleeding risks will be extracted. In this study, predetermined high bleeding risks are 1) patients with hypertension diagnosis, 2) patients with liver dysfunction, 3) patients with renal dysfunction diagnosis, 4) patients with a history of bleeding, 5) patients with hemorrhagic stroke, 6) patients with alcohol abuse, 7) patients with concomitant used of antiplatelet drugs, 8) patients with chronic (continuously for longer than 90 days) concomitant use of Non-steroidal antiinflammatory drug (NSAID), 9) highly elderly (> 80 years old), 10) patients with refractory hypertension, 11) patients with a history of peptic ulcer diagnosis, 12) patients with active cancer, 13) patients with diabetes mellitus, 14) patients whose body weight is <40kg, 15) patients with polypharmacy (sea Section 5.4 for the definition). Patients with at least one predetermined high bleeding risk factor will be divided into two cohorts, apixaban and warfarin cohorts, based on the first prescribed drug just after the NVAF diagnosis. Patient characteristics will be balanced by using an inverse probability of treatment weighting (IPTW) method to create balanced apixaban and balanced warfarin cohorts. Comparisons will be conducted by using these balanced warfarin and apixaban cohorts (Kaplan-meier curves, incidence rates per 1,000 person-year and hazard ratio with 95% confident intervals). The primary safety and effectiveness analyses are comparison of apixaban with warfarin in patients with at least one predetermined risk factor for bleeding.

- Second, after the first analysis, we will conduct separate interaction analysis of the treatment (apixaban vs. warfarin) and one of the 15 risk factors (e.g., hypertension yes vs no, etc) to see if treatment effects are consistent among patients with or without each specific factor
- Third, patients will be stratified by risk factors into 15 subgroups, and same IPTW analyses as described in the step 1 will be conducted only in the subgroups with adequate sample sizes.

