2.2.4. Objectives of other exploratory analysis are

To explore the risk of major bleeding and stroke/SE in the specific populations at higher bleeding risk(s).

As shown above (see 2.1), after interaction analyses of the treatment and risk factors, patients will be stratified to subgroups by each of above mentioned 15 predetermined risk factors separately. Subgroups with adequate sample size will be selected for IPTW analyses.

In the previous feasibility analysis, we found that the numbers of patients with hemorrhagic stroke, alcohol abuse, chronic concomitant used of NSAIDs (for continuously > 90 days), and refractory hypertension were less than 2,000. Due to the insufficient statistical power, these subgroups could be eliminated from the further subgroup analysis. Again, the final decision will be based on the formal evaluation of the number of sample sizes N in those subgroups.

Candidates of exploratory subgroups listed based on the preliminary feasibility analysis

- Exploratory analysis regarding hypertension
- *Exploratory analysis regarding liver dysfunction.*
- Exploratory analysis regarding renal impairment.
- *Exploratory analysis regarding bleeding including intracranial hemorrhage*
- Exploratory analysis regarding concomitant use of antiplatelet drug
- *Exploratory analysis by age*
 - \checkmark > 80 y
 - \checkmark >90 y
- Exploratory analysis regarding peptic ulcer
- Exploratory analysis regarding active cancer
- *Exploratory analysis regarding low body weight (<40kg)*
- Exploratory analysis regarding diabetes mellitus
- *Exploratory analysis regarding polypharmacy (≥6 medicines)*

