Cancer diagnosis	Baseline characteristic Sub-group identifier	Baseline period	Dichotomous variable equals 1 if there are ≥1 diagnoses for diabetes mellitus ICD-10 or disease codes during the baseline period.
Treated with antiplatelet drug	Baseline characteristic	Baseline period	Dichotomous variable equals 1 if there are ≥1 prescriptions of antiplatelet drug ATC or receipt codes during the baseline period.
Treated with antiplatelet drug (>28 d)	Sub-group identifier	Baseline period	Dichotomous variable equals 1 if there are ≥1 prescriptions of antiplatelet drug ATC or receipt codes during the baseline period.
Treated with NSAIDs	Baseline characteristic	Baseline period	Dichotomous variable equals 1 if there are ≥1 prescriptions of NSAIDs ATC or receipt codes during the baseline period.
Treated with NSAIDs (>90 d)	Sub-group identifier	Baseline period	Dichotomous variable equals 1 if there are ≥1 prescriptions of NSAIDs ATC or receipt codes during the baseline period.
Treated with gastric secretion inhibitor	Baseline characteristic	Baseline period	Dichotomous variable equals 1 if there are ≥ 1 prescriptions of gastric secretion inhibitor drug ATC or receipt codes during the baseline period.
Treated with statin- based drug	Baseline characteristic	Baseline period	Dichotomous variable equals 1 if there are ≥1 prescriptions of statin-based drug ATC or receipt codes during the baseline period.
Treated with anti- hypertensives	Baseline characteristic	Baseline period	Dichotomous variable equals 1 if there are ≥1 prescriptions of anti-hypertensive ATC or receipt codes during the baseline period.
Treated with anti- arrhythmics	Baseline characteristic	Baseline period	Dichotomous variable equals 1 if there are ≥1 prescriptions of anti-arrythmics ATC or receipt codes during the baseline period.
Treated with beta- blockers	Baseline characteristic	Baseline period	Dichotomous variable equals 1 if there are ≥ 1 prescriptions of beta-blockers ATC or receipt codes during the baseline period.
Treated with heparins	Baseline characteristic	Baseline period	Dichotomous variable equals 1 if there are ≥ 1 prescriptions of heparins ATC or receipt codes during the baseline period.
Cardioversion	Baseline characteristic	Baseline period	Dichotomous variable equals 1 if there is ≥1 operation of cardioversion receipt codes during the baseline period.

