Alcohol abuse	Sub-group identifier	Baseline period	Dichotomous variable equals 1 if there are ≥1 diagnoses for Alcohol abuse ICD-10 or disease codes during the baseline period.
Bleeding diagnosis	Sub-group identifier	Baseline period	Dichotomous variable equals 1 if there are ≥1 diagnoses for major or any bleeding ICD-10 or disease codes during the baseline period

Variable	Role	Data source(s)	Operational definition	
Peptic ulcer diagnosis	Sub-group identifier	Baseline period	Dichotomous variable equals 1 if there are ≥1 diagnoses for peptic ulcer ICD-10 or disease codes during the baseline period	
Hemorrhagic stroke diagnosis	Sub-group identifier	Baseline period	Dichotomous variable equals 1 if there are ≥1 diagnoses for hemorrhagic stroke ICD-10 or disease codes during the baseline period	
Low body weight (<40 kg)	Sub-group identifier	Baseline period	Body weight during baseline period	
Polypharmacy	Sub-group identifier	Baseline period	Dichotomous variable equals 1 if there are ≥ 6 prescriptions of oral drug ATC or receipt codes during the baseline period.	
PT-INR (Prothrombin time- international normalized ratio)	potential confounder	Baseline period	Continuous variable. * Only available for patients treated with warfarin	
Physician specialty	potential confounder	Index date	Dichotomous variable equals 1 if a physician specialty on the index date is categorized into a cardiac specialty and 0 if others. Following specialties will be categorized as the cardiac specialty: cardiology stroke, cardiovascular surgery, pediatric cardiology, neurosurgery, cardiovascular medicine, and neurology. If there are ≥ 1 specialties but including the cardiac specialty, the physician specialty will be regarded as the cardiac specialty.	
Hospital size (<500 beds or not)	potential confounder	Index date	Dichotomous variable equals 1 if hospital size on the index date is <500 beds and 0 if ≥500 beds.	
Hospitalization status on index date	potential confounder	Index date	Dichotomous variable equals 1 if hospitalization status is inpatient and 0 if outpatient.	
INR (warfarin cohort)	Baseline characteristic	Baseline period	Continuous variable. * Only available for patients treated with warfarin	
Apixaban dose (2.5 g BID)	Baseline characteristic	Baseline period	2.5 mg BID or 5mg BID * Only available for patients treated with apixaban	

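### Four SAP 5.4 definitions (NSAIDs >90 d, polypharmacy, antiplatelet >28 d, cancer) do not match the factors they should implement

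*SAP*

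**What the plan says.** SAP 2.1 lists 15 bleeding-risk factors. Having at least one admits a patient to the primary population. Step 2 then runs a "separate interaction analysis of the treatment (apixaban vs. warfarin) and one of the 15 risk factors", and step 3 analyses subgroups of adequate size. SAP 5.4 gives the operational definitions.

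- **NSAIDs.** Factor 8 in SAP 2.1 is "patients with chronic (continuously for longer than 90 days) concomitant use of Non-steroidal antiinflammatory drug (NSAID"). Protocol 8 and 9.1 say the same, and SAP 2.2.4 repeats the 90-day continuous threshold. In 5.4, the row labelled NSAIDs (>90 d) equals 1 if there are "≥1 prescriptions of NSAIDs ATC or receipt codes during the baseline period". The any-use NSAID row has identical wording.
- **Polypharmacy.** SAP 2.1 lists "patients with polypharmacy (sea Section 5.4 for the definition"), so 5.4 governs entry for this factor. The 5.4 row requires "≥ 6 prescriptions of oral drug ATC or receipt codes during the baseline period". SAP 2.2.4 speaks of at least 6 medicines and SAP 4.4 of at least 6 concomitant drugs.
- **Antiplatelet drugs.** The 5.4 row labelled >28 d repeats the any-use antiplatelet row. SAP 4.4 labels the subgroup >28 d. Factor 7 in SAP 2.1 states no duration.
- **Cancer.** The 5.4 row refers to diabetes mellitus codes. Appendix 10.3.1 has a separate cancer code list, and Appendix 10.3.6 sends active cancer to it.

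For antiplatelet drugs, NSAIDs and polypharmacy, Appendix 10.3.6 only refers back to 5.4.

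**The concern.** The table in 5.4 is what a programmer will code from, and for the three drug factors no other part of the SAP gives an algorithm. The thresholds intended for NSAIDs and antiplatelet drugs can be seen in the labels and in other sections. What is missing is a rule that applies them: an allowed gap, cumulative versus continuous supply, and, for polypharmacy, whether drugs or prescriptions are counted.

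At stake is which patients the results describe. NSAID and polypharmacy status can decide entry to the primary population, and each defines a step 2 interaction variable. Polypharmacy, antiplatelet use and cancer are also planned exploratory subgroups.

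**Working it through.** The SAP states no figure to reproduce here. The check sets the definitions side by side and then asks how far apart they lie.

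| Factor | Rule in SAP 5.4 | Rule elsewhere | Where it matters |
|---|---|---|---|
| NSAIDs (>90 d) | at least 1 prescription | continuous, over 90 days (SAP 2.1, 2.2.4; protocol 8, 9.1) | primary entry, step 2 |
| Polypharmacy | at least 6 oral-drug prescriptions | at least 6 medicines (2.2.4) or concomitant drugs (4.4) | primary entry, step 2, subgroup |
| Antiplatelet (>28 d) | at least 1 prescription | over 28 days (row label, 4.4); no duration in 2.1 | subgroup only |
| Cancer | diabetes codes | cancer codes (10.3.1 via 10.3.6) | copy error |

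The baseline is 180 days (SAP 4.1.1). The documents give no supply lengths, so those below are assumptions.

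**NSAIDs.** Smallest n with n × s > 90, where s is days of supply per prescription:
- s = 14: 6 × 14 = 84, 7 × 14 = 98, so n = 7
- s = 30: 3 × 30 = 90, 4 × 30 = 120, so n = 4
- s = 60: 2 × 60 = 120, so n = 2
- s = 90: 1 × 90 = 90, 2 × 90 = 180, so n = 2

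SAP 5.4 asks for n = 1 in every case.

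**Polypharmacy, refills counted.** Prescriptions per drug = 180 / refill interval; drugs needed = 6 / prescriptions per drug:
- 30 days: 180/30 = 6, and 6/6 = 1 drug
- 60 days: 180/60 = 3, and 6/3 = 2 drugs
- 90 days: 180/90 = 2, and 6/2 = 3 drugs

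The rule can also miss patients. Five oral drugs with one prescription each, plus one non-oral drug, make 6 concomitant drugs but only 5 oral prescriptions. The net direction is therefore unknown.

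**Polypharmacy, distinct codes counted.** One refilled drug no longer qualifies. Six consecutive 30-day courses of different drugs (6 × 30 = 180 days) still do, with only one drug in use at a time. Concurrency and the oral-only scope remain in conflict with 4.4.

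**Antiplatelet.** Smallest n with n × s > 28:
- s = 14: 2 × 14 = 28, 3 × 14 = 42, so n = 3
- s = 28: 2 × 28 = 56, so n = 2
- s = 30: n = 1

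The two rules differ only for patients with 28 days of supply or less in total or, if continuous use is meant, without an unbroken run over 28 days.

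**Reach into the primary analysis.** A patient with any of the other 14 factors is in the primary population under either rule. The NSAID or polypharmacy wording changes membership only for patients with none of the other listed factors. The propensity covariates in SAP 7.1.1 use any NSAID use and any antiplatelet use; the >90 d, >28 d, polypharmacy and cancer variables are not in that list.

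**The case against.** The strongest defence is that 5.4 often puts thresholds in the row label. The age row is defined simply as age at the index date, and the low-weight row as body weight in baseline; nobody would read these as any age or any weight. On that convention the >90 d and >28 d rows are merely incomplete. The feasibility count below 2,000 in SAP 2.2.4 is described as continuous use over 90 days, so the team evidently had that threshold in mind. This shows intent but does not rescue the rows. The age and weight rows name a quantity to which the label's cut-off can be applied. The NSAID and antiplatelet rows state a complete yes/no rule, and that rule is the any-use one.

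On polypharmacy, the refractory-hypertension row uses similar phrasing to count drugs, so six distinct codes is a fair reading. That stands: the figures of one to three drugs hold only if refills are counted.

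A reader might infer more than the documents support:
- **That short-term NSAID users enter the primary population wholesale.** Most listed factors have no connection with NSAID use, among them hypertension, diabetes and age over 80. Patients with any of these are included regardless.
- **That an NSAID subgroup result would be wrong.** Protocol 8 says of this and three other small groups that "we will not include these subgroups for the future analysis". SAP 2.2.4 is looser ("the final decision will be based on the formal evaluation of the number of sample sizes N in those subgroups"), but NSAIDs are absent from its candidate list, from the 4.4 table and from the 7.2.3 summary. The effect is nominal.
- **That the cancer subgroup would be the diabetes subgroup.** This follows only from the literal row, and the two appendices show what was meant.
- **That the primary hazard ratio is biased.** Nothing in the documents shows this. SAP 3.2 also treats the subgroup analyses as exploratory.

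**Conclusion.** The point holds as a set of definitions that are wrong as written, and they should be fixed before programming. NSAIDs (>90 d) and polypharmacy matter most. Followed literally, both change the step 2 interaction variables, and both change primary-population membership for patients who have none of the other factors. Polypharmacy also changes its own subgroup. The antiplatelet row affects only an exploratory subgroup, and the cancer row is a recoverable copy error.

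The number of patients affected cannot be computed, because the documents give neither supply lengths nor the overlap between factors. That the change in the primary population is probably small is a judgement, resting on how many other factors admit a patient. The prescription counts above rest on assumed supply and refill lengths.

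**What to change.** Edit four rows of SAP 5.4:

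1. Code NSAIDs (>90 d) on continuous days of supply over 90, with the allowed gap stated.
2. Code antiplatelet (>28 d) on days of supply over 28, stating whether cumulative or continuous.
3. Code polypharmacy on at least 6 distinct drugs rather than prescriptions. The sponsor should state the concurrency window and whether only oral drugs count. Align 2.2.4 and 4.4 with this row; 2.1 already defers to 5.4.
4. Point the cancer row to the cancer codes in Appendix 10.3.1.

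Then re-count the primary population and the subgroups before analysis, so that the rules are settled before results are seen.

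The cost is a short table edit, aligned wording in two sections, and re-run counts. SAP 4.1.3.1 already uses days of supply for apixaban and warfarin follow-up. The net change in patient numbers is not known in advance.

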6. HANDLING OF MISSING VALUES

Patients without all required data will be excluded from the analysis.

7. STATISTICAL METHODOLOGY AND STATISTICAL ANALYSES

7.1. STATISTICAL METHODS

7.1.1. Calculation of Propensity Score

In this study, balanced cohorts (apixaban vs. warfarin) will be created by an IPTW method. Propensity scores will be estimated by unconditional logistic regression analyses that incorporate potential predictors of therapy as independent variables in the regression and cohort status as the outcome. Using calculated propensity score an IPTW method will be applied to balance the warfarin and apixaban cohorts, which will be used for the comparisons of all endpoints (sections 5.1 and 5.2). The following covariates will be included in the logistic regression for calculation of propensity score:

• age on index date

- gender
- CHADS2 score in baseline
- CHA2DS2-VASc score in baseline
- heart failure diagnosis in baseline
- coronary heart disease diagnosis in baseline
- peripheral arterial disorder diagnosis in baseline
- myocardial infarction diagnosis in baseline
- hyperthyroidism or thyrotoxicosis in baseline
- TIA diagnosis in baseline
- stroke or SE diagnosis in baseline
- renal dysfunction diagnosis in baseline
- liver dysfunction diagnosis in baseline
- bleeding diagnosis in baseline
- hypertension diagnosis in baseline
- diabetes mellitus diagnosis in baseline
- treated with antiplatelet drug in baseline
- treated with NSAIDs in baseline
- treated with gastric secretion inhibitor in baseline
- treated with statin-based drug in baseline
- treated with anti-hypertensives in baseline
- treated with anti-arrhythmics in baseline
- treated with beta-blockers in baseline
- treated with heparins in baseline
- cardioversion in baseline

The operational definitions for the above covariates are shown in the Section 5.4.

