9.2.1. Inclusion criteria

Patients must meet all of the following inclusion criteria to be eligible for inclusion in the study:

- 1. Diagnosed with AF anytime in the baseline period or on the index date, also have definitive diagnosis of AF anytime in the baseline period, on the index date, or post-index period.
- 2. Prescribed apixaban or wararin on or after the day of AF diagnosis. The first observed prescription will be used to identify the patient's index date and treatment cohort
- 3. No use of the any OACs during the baseline period (the 180 days before the index date)
- 4. Age of 18 years or older on the index date.

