2. INTRODUCTION

Atrial fibrillation (AF) is characterized by a rapid, irregular heartbeat which can cause blood to pool in the atria and increase the risk of the formation of blood clots. AF affects 0.6% to 1.6% of the general population and up to 14% in cardiovascular clinics in Japan¹⁻³. AF can be categorized into three main categories based on patient characteristics: lone atrial fibrillation -AF in the absence of overt cardiovascular disease or precipitating illness non-valvular AF (NVAF) – presence of AF without concurrent rheumatic mitral valve disease or history of mitral valve repair or prosthetic heart valve; and secondary AF-AF that occurs in the setting of acute myocardial infarction (MI), cardiac surgery, pericarditis, myocarditis, hyperthyroidism, pulmonary embolism, pneumonia, or other acute pulmonary disease. Anticoagulation therapy is important to prevent thromboembolism in patients with NVAF. Warfarin, a vitamin K antagonist, is the first oral anticoagulant approved for the treatment and prevention of thromboembolism in Japan in 1962 and it had long been the only oral anticoagulant until the first non-vitamin K antagonist oral anticoagulants (NOACs), dabigatran, was introduced with approval for NVAF treatment in March 2011⁴. Apixaban was approved in December 2012 in Japan and demonstrated superiority compared to warfarin in preventing stroke or systemic embolism, caused less bleeding, and resulted in lower mortality in patients with atrial fibrillation in Phase 3 clinical trial⁵.

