2.1. STUDY DESIGN

This is a retrospective observational study using data from Medical Data Vision Co. Ltd. (MDV Co. Ltd.) database (data set from 1 March, 2011 to 31 Jun, 2021). Among patients registered in the database, patients are selected based on the inclusion and exclusion criteria (see below).

Study measures include: (1) for safety evaluation: major bleeding (primary safety endpoint, defined as any bleeding requiring hospitalization for treatment); (2) for effectiveness evaluation: a composite of ischemic stroke, hemorrhagic stroke or SE (primary effectiveness endpoint).

The primary purpose of this study is to investigate the safety and effectiveness of apixaban compared to warfarin in patients who are prone to bleeding, with at least one known risk factor for bleeding. The analyses will be conducted using the 3-step procedure shown below,

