2.1.3. Treatment/cohort labels

For primary analysis,

- IPTW-balanced apixaban cohort: NVAF patients de novo diagnosis with NVAF and initiate apixaban and have at least one risk factor(s) of bleeding.
- IPTW-balanced warfarin cohort: NVAF patients de novo diagnosis with NVAF and initiate warfarin and have at least one risk factor(s) of bleeding.

Patients will be assigned to each cohort based on the first prescription of oral anticoagulants after the diagnosis of NVAF (warfarin or apixaban). If the 1st prescribed oral anticoagulants are not warfarin

nor apixaban, the patients will be excluded. Patient clinical and demographic characteristics will be balanced by using IPTW methods.

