4.1.1. Inclusion criteria

Patients must meet all of the following inclusion criteria to be eligible for inclusion in the study:

- 1. Patients with diagnosis with NVAF anytime in the baseline period or on the index date,
- 2. The first prescribed anticoagulant is apixaban or warfarin after the index date.
- 3. No use of the any oral anticoagulants (OACs) during the baseline period (the 180 days before the index date)
- 4. Age of 18 years or older on the index date.

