4.1.3.2. Index date

The date when patients initiated warfarin or apixaban

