7.1.2. Inverse probability treatment weighting (IPTW)

IPTW with stabilized weights will be used to balance patient characteristics between two groups using propensity score calculated by using a multivariable logistic model as mentioned above (see above 7.1.2.1). However, if a treated patient has a very low propensity score, a very large weight can be created, which leads to increased variability of the estimated treatment effect. In order to address this, the weights can be stabilized by using a formula shown below, by multiplying the treatment and control weights by a constant, equal to the expected value of being in the treatment or comparison cohorts, respectively.

 $W_i = \frac{Z}{PS_i} + \frac{1-Z}{1-PS_i}$, z: probability of treatment without considering covariates

The distribution of the stabilized weight will be reviewed. If there are extreme outliers, the large weights could be set to a less extreme value (e.g. recoding all weights that are outside 5th and 95th percentile). If needed, truncation can be done after stabilizing the weights. After the weights are applied, the balance of the baseline covariates will be assessed. First, the means and proportions of baseline variables are compared. The standardized difference compares the difference in means in units of the standard deviation. If the standardized difference is less than 10%, the covariates are considered balanced.

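### No earliest index date and no calendar term: 461 to 491 of 3,595 possible index days (12.8% to 13.7%) can supply only warfarin starters

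*SAP*

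**What the plan says.** **Data window and approval.** SAP 2.1 and protocol 9.1 use the same extract: "data set from 1 March, 2011 to 31 Jun, 2021". The SAP Introduction and protocol 7 both give the approval month: "Apixaban was approved in December 2012 in Japan".

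**Index date and cohort.** SAP 4.1.3.2 defines the index date as "The date when patients initiated warfarin or apixaban". Protocol 9.2.1 says "The first observed prescription will be used to identify the patient's index date and treatment cohort". SAP 2.1.3 adds that "Patients will be assigned to each cohort based on the first prescription of oral anticoagulants after the diagnosis of NVAF". The only time condition on entry is the look-back in SAP 4.1.1: "No use of the any oral anticoagulants (OACs) during the baseline period (the 180 days before the index date". The inclusion and exclusion criteria of both documents contain no calendar limit.

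**Adjustment.** SAP 7.1.1 states "The following covariates will be included in the logistic regression for calculation of propensity score" and lists 25 items covering demographics, risk scores, diagnoses, co-medication and cardioversion. Index date, index year and calendar period are absent from this list and from the variable table in SAP 5.4. After weighting, SAP 7.1.2 says "the balance of the baseline covariates will be assessed", and 7.1.6 adds any unbalanced variable to the Cox model. The only sensitivity analysis, in 7.1.8, is the E-value.

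**The concern.** Propensity weighting compares patients who could have received either drug. Before apixaban was approved, the probability of starting it was zero. The 7.1.1 model does not know the date, so it gives those warfarin starters a score based on age, comorbidity and co-medication, as if apixaban had been an option. Positivity fails in a stratum that can be identified exactly from the index date, and the plan keeps that stratum in.

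The two primary hazard ratios (major bleeding and stroke/SE) would then compare apixaban with a warfarin arm drawn partly from years that have no apixaban counterpart. Any change over those years in event rates, care or coding that the 25 covariates do not capture would load onto the warfarin arm alone.

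**Working it through.** **Inputs.** Data start on 1 March 2011 (SAP 2.1). The stated data end, 31 June 2021, does not exist and is read as 30 June 2021. The look-back is 180 days (SAP 4.1.1). Approval is December 2012 with no day given, so 1 and 31 December are used as the range.

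**Length of the warfarin-only window.**
- Earliest index date with a full look-back: 1 March 2011 + 180 days = 28 August 2011.
- 28 August 2011 to 1 December 2012 = 461 days; to 31 December 2012 = 491 days.
- 28 August 2011 to 30 June 2021, inclusive = 3,595 days.
- Share: 461/3,595 = 12.8%; 491/3,595 = 13.7%.
- If a full look-back inside the data is not enforced, the window is 641 to 671 days, so 461 to 491 is a minimum.

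This is a share of calendar days. Neither document gives warfarin starts by year, so the share of patients cannot be derived.

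**Can any planned check see it?**
- Weight review and truncation (7.1.2) act on extreme weights. These patients get ordinary scores and so ordinary weights.
- Standardized differences (7.1.2 to 7.1.4) and the Cox fallback (7.1.6) act on listed variables. The summary tables in 7.2.3 refer to 5.4 for covariates, but calendar time is not in 5.4.
- The E-value (7.1.8) says how strong an unmeasured confounder would have to be. It does not test for this one.
- Protocol 9.9 concedes residual differences in general terms. The index date is in the data, so this one is avoidable.

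**What it could do (illustration; all inputs assumed).** Let q be the pre-approval share of weighted warfarin person-time, and r the ratio of the early to the later warfarin event rate that remains after weighting. With a true hazard ratio of 1, the apparent value is 1/((1−q) + q·r).

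| q | r = 0.8 | r = 1.5 |
|---|---|---|
| 5% | 1.010 | 0.976 |
| 13% | 1.027 | 0.939 |
| 14% | 1.029 | 0.935 |
| 25% | 1.053 | 0.889 |

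The documents support no particular q or r. If r = 1 there is no bias at any q.

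**Cost of a restriction in power.** The SAP's own calculation reproduces first. Events = 4(1.960 + 0.842)²/(ln 0.7)² = 246.8 (stated 246). Patients = 246/((3.77% + 2.50%)/2) = 7,846.9 (stated 7,846) and 246/((2.77% + 1.79%)/2) = 10,789.5 (stated 10,789). Dividing events by an annual rate implies one person-year per patient.

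For the restricted cohorts, events per arm = N(1 − exp(−rate × t)), with t = 1 year, warfarin rates 3.77% and 2.77%, apixaban rates 0.7 times these, and apixaban N = 10,000. Power = Φ(√(D·p·(1−p))·|ln 0.7| − 1.96), where D is total events and p is the warfarin share of patients. No variance inflation from weighting is included.

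| Warfarin N | Loss | Bleeding | Stroke/SE |
|---|---|---|---|
| 10,000 | none | 99% | 97% |
| 8,700 to 8,600 | 13% to 14% | 99% | 96% |
| 6,000 | 40% | 97% | 90% |

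**The case against.** **No bias is demonstrated.** This stands. A warfarin arm that includes earlier patients distorts the hazard ratio only if outcome risk differs by period after weighting, and period differences that act through the listed case-mix and co-medication are already adjusted. A reader might infer that the results will be materially biased, or biased in favour of apixaban. The documents give no patient count by period and no secular trend, so neither inference is supported.

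**The plan has general safeguards.** The E-value covers any unmeasured confounder, calendar period included, and protocol 9.9 admits residual differences. Both are true, but neither removes patients who had no access to apixaban.

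**Three further confounders.** SAP 5.4 labels physician specialty, hospital size and hospitalization status on the index date as potential confounders, and 7.1.1 omits them. A reader might infer that they go uncontrolled. The text does not bear that out: 7.1.2 to 7.1.4 check balance on baseline variables, 7.1.6 adds unbalanced ones to the Cox model, and the tables in 7.2.3 point to 5.4 for the Cox covariates. That route is suggested but not stated, so it needs only a clarification. The fourth variable so labelled, PT-INR, exists for warfarin patients only and cannot enter a propensity model.

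**A restriction might leave the study underpowered.** Power below 80% can be produced by assuming half a year of follow-up per patient, but stroke/SE power is then already 78% with no loss at all. That shortfall comes from the follow-up assumption, not from the restriction. The plan allows up to two years, and SAP 7.1.9 reports more than 10,000 patients in each cohort.

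**Conclusion.** The point holds as a design gap that is cheap to close. As written, the plan admits warfarin starters from at least 461 to 491 of 3,595 possible index days (12.8% to 13.7%) on which apixaban could not be started, and no planned check can detect or correct this. The figure rests on reading the data end as 30 June 2021, on approval falling between 1 and 31 December 2012, and on a full 180-day look-back. It measures calendar time and not patients. The size and direction of any effect on the two primary hazard ratios are unknown. The three additional variables are a matter of wording only.

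**What to change.** 1. In protocol 9.2 and SAP 4.1, restrict index dates in both cohorts to after apixaban became available, with the December 2012 approval as the earliest possible floor.
2. After that restriction, add index year to the 7.1.1 model and to the 7.1.2 balance check. The order matters: index year alone, without the floor, would drive pre-approval scores towards zero and would not restore positivity.
3. Re-run the feasibility counts behind SAP 7.1.9 and the subgroup sizes in SAP 2.1 and 2.2.4 on the restricted cohorts.
4. As a clarification, state whether physician specialty, hospital size and hospitalization status belong to the propensity model or to the balance check.

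The cost is a protocol amendment to 9.2, edits to SAP 4.1, 5.4, 7.1.1 and 7.1.2, and a repeat of the counts. No new data are needed. The price is the loss of the earliest warfarin starters and possibly more variable weights. On the stated assumptions, power stays at or above 90% for both endpoints even after a 40% warfarin loss. The actual loss is unknown, which is why step 3 is needed.
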